10.2.4 Treatment-Emergent Adverse Events per Patient-Years of Exposure

Not applicable.

10.2.5 SAEs (Including Deaths) and Adverse Events Leading to Study Drug Discontinuation

Serious AEs (including deaths) and AEs leading to study drug discontinuation will be summarized by SOC and PT and in listing format.

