Study Population and Number of Subjects to be Enrolled:	Approximately 600 healthy subjects with moderate to severe GL will be enrolled. Enrollment will be approximately balanced for moderate and severe GL severity at maximum frown. At least 60% of subjects will be enrolled with a baseline FLO-11 questionnaire transformed total score ≤50.	
Investigational Plan:	This is a 12-week, multicenter, Phase 3 study designed to evaluate the safety and efficacy of AGN-151586 treatment in adult subjects with moderate to severe GL. Eligible subjects will receive 1 double-blind treatment of either AGN-151586 or placebo on Baseline Day 1 and, if they meet retreatment criteria, 1 open-label treatment with AGN-151586 at Day 43.	
Key Eligibility Criteria:	Adult male or female, ≥ 18 years of age, having moderate or severe GL at maximum frown (as assessed by the evaluating investigator and subject using the FWS at Screening and Baseline Day 1). The investigator and subject ratings must match within a visit but do not have to match between Screening and Baseline Day 1.	
Study Drug and Duration of Treatment:	Based upon randomization, on Baseline Day 1, subjects will receive either AGN-151586 or placebo (3:1 randomization ratio) administered as 5 intramuscular injections in the glabellar complex. Randomization will be stratified by investigator site, toxin use history (for aesthetic purpose), and baseline GL severity at maximum frown (the scores from the investigator and subject must match on Baseline Day 1 per eligibility criteria). Based on meeting the retreatment criteria, subjects may also receive an open-label treatment with of AGN-151586 on Day 43.	
Date of Protocol Synopsis:	01 August 2022	

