4 INVESTIGATIONAL PLAN

4.1 Overall Study Design and Plan

This is a 12-week, multicenter, Phase 3 study designed to evaluate the safety and efficacy of AGN-151586 in treating GL. Subjects are adults (≥ 18 years of age) with moderate to severe GL at maximum frown as assessed independently by both the investigator and subject using the FWS. The investigator and subject ratings for GL will be done at the Screening Visit and at the Baseline Day 1 Visit. The investigator and subject ratings must match within a visit but do not have to match between Screening and Baseline Day 1. Each eligible subject may receive up to 2 study treatments with AGN-151586. The time of study treatment administration defines Hour 0 for the treatment period (on Day 1 for double-blind period and on Day 43 for open-label period).

Eligible subjects will be enrolled into the study containing 2 treatment periods:

Double-blind Period: Screening will occur up to 14 days prior to Baseline Day 1. Randomization and treatment will occur on Baseline Day 1 after all other study procedures have been completed. A single treatment of AGN-151586 or placebo will be administered on Baseline Day 1, based on randomization (3:1 ratio of AGN-151586:placebo). Randomization will be stratified by investigator site, toxin use history (for aesthetic purpose), and baseline GL severity at maximum frown. All enrolled subjects will receive treatment on Baseline Day 1 and attend in-clinic site visits to fully characterize the onset of treatment effect. Thereafter, in-clinic site visits will be completed to characterize the peak and duration of effect.

The double-blind period will end on Day 43. The Day 43 visit will occur 42 ± 2 days following the Day 1 visit. The study assessments conducted during the Day 43 visit serve as the final assessment for the double-blind period and as the baseline assessment for the open-label period.

Open-label Period:

For subjects meeting all the retreatment criteria on Day 43, a single open-label treatment with AGN-151586 will be administered on the same day. The subject will then be followed for approximately 6 weeks (through Day 84). The schedule of the follow-up visits in the open-label period is the same as that in the double-blind period. After each study treatment administration, subjects must remain in the clinic for at least 30 minutes for observation of any AEs.

Retreatment is only permitted on the Day 43 visit.

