5.5 Prior and Concomitant Therapy

5.6 Withdrawal of Subjects and Discontinuation of Study

A subject can voluntarily withdraw at any time or will be withdrawn from the study for reasons including, but not limited to, the following:

- Clinically significant abnormal laboratory results or AEs, which rule out continuation of the study drug, as determined by the investigator or the Sponsor. However, when possible, the subject is encouraged to remain in the study for all safety follow-up assessments, even if the subject does not meet retreatment criteria.
- The investigator believes it is in the best interest of the subject.
- The subject requests withdrawal from the study.

- Eligibility criteria violation was noted after the subject started study drug and continuation of the study drug would place the subject at risk.
- Introduction of prohibited medications or dosages and continuation of the study drug would place the subject at risk.
- Subject is significantly noncompliant with study procedures.
- If the subject does not meet the GL severity criterion at Day 43 visit for retreatment, the subject will be followed weekly per the visit schedule (Appendix D) until the FWS grades assessed by both investigator and subject have returned to moderate or severe (investigator and subject grades do not need to match) before being discontinued from the study by completing either the Early Exit or Study Exit Visit.
- If the subject becomes pregnant, then study drug will not be administered, and the subject can either be discontinued from the study after Early Exit Visit procedures are completed or remain in the study for all safety follow-up assessments. If a pregnancy occurs in a study subject, information regarding the pregnancy and the outcome will be collected.
- If the subject declines retreatment despite meeting the retreatment criteria at Day 43 visit, the subject will be discontinued from the study after Early Exit Visit procedures are completed unless the investigator determines the subject should remain in the study for safety follow-up.

For subjects to be considered lost to follow-up, reasonable attempts must be made to obtain information on the subject's final status. At a minimum, 2 telephone calls must be made and 1 certified letter must be sent and documented in the subject's source documentation.

The following events, if applicable, will also cause premature termination of the clinical study:

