10.0 Safety Analyses

10.1 General Considerations

Safety data will be summarized for the Safety Population. Safety summaries will be presented by treatment group, by overall study, by study period, and by treatments received in the DB Period and in the OL Period (i.e., AGN-151586/AGN-151586, AGN-151586/None, Placebo/AGN-151586, Placebo/None).

For the safety analysis, subjects are assigned to a treatment group based on the treatment actually received, regardless of the treatment randomized.

The safety parameters will include AEs, vital signs, 12-lead ECGs, laboratory evaluations (hematology and chemistry), neurological assessment (including examination of cranial nerves II through VII), and presence of antidrug antibodies. For change from baseline safety parameters, “baseline” refers to the last non-missing observation before the first study drug administration in the study.

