10.2.2 Adverse Event Overview

An overview of AEs will be presented consisting of the number and percentage of subjects experiencing at least one event for each of the following AE categories:

- Any TEAE
- Any TEAE related to study treatment according to the investigator
 - Any TEAE related to study drug according to the investigator
 - Any TEAE related to study procedure according to the investigator
- Any mild TEAE
 - Any mild TEAE related to study treatment according to the investigator
- Any moderate TEAE
 - Any moderate TEAE related to study treatment according to the investigator
- Any severe TEAE
 - Any severe TEAE related to study treatment according to the investigator
- Any serious TEAE
 - Any serious TEAE related to study treatment according to the investigator
- Any TEAE leading to discontinuation of study drug
- Any TEAE leading to death

- Any PDSOT TEAE
- Any neurological assessment associated TEAE
- All deaths

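### The adverse-event tables count only withdrawal from study drug, so on the literal reading the open-label row is essentially zero, and no table or listing shows which events led subjects to leave the study

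*SAP*

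**What the plan says.** **Adverse-event tables.** The overview in SAP 10.2.2 includes the category "Any TEAE leading to discontinuation of study drug", and Protocol 7.5 has the same one. SAP 10.2.5 adds that "Serious AEs (including deaths) and AEs leading to study drug discontinuation will be summarized by SOC and PT and in listing format". Neither document has a category, table or listing for treatment-emergent adverse events (TEAEs) that led a subject to leave the study. SAP 10.1 states: "Safety summaries will be presented by treatment group, by overall study, by study period". The open-label period will therefore have its own version of this row.

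**Dosing.** Protocol 4.1 says: "A single treatment of AGN-151586 or placebo will be administered on Baseline Day 1". For subjects who meet the retreatment criteria on Day 43, "a single open-label treatment with AGN-151586 will be administered on the same day". It then closes the door on anything later: "Retreatment is only permitted on the Day 43 visit". The Synopsis describes the Day 1 treatment as "administered as 5 intramuscular injections in the glabellar complex".

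**Leaving the study.** Protocol 5.6 opens with: "A subject can voluntarily withdraw at any time or will be withdrawn from the study for reasons including, but not limited to, the following". The first reason on its list is laboratory findings or adverse events that make further study drug unsuitable, and it encourages those subjects to stay for safety follow-up where possible. Protocol 5.7 names stopping treatment and stopping participation as separate events.

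**Disposition and exposure.** SAP 5.0 summarizes premature study discontinuation with the reason, by treatment group and by period. SAP 6.0 takes time on treatment to run to the end of the period or to study exit, and says that an incomplete dose will be flagged.

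**The concern.** A discontinuation-of-drug category suits a drug taken repeatedly, where stopping it is a visible consequence of poor tolerability. Here the drug is given in one session per period. After the Day 43 session there is nothing left to stop, so the row no longer measures tolerability in the open-label period.

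That period supplies the repeat-treatment data, and Protocol 3.1 makes acceptable safety after repeat as well as single treatment part of the clinical hypotheses. Protocol 4.2 says the period has no control group, so its descriptive tables carry the evidence. A reader of the study report who sees no open-label events under this row could take it to mean that nobody left because of an adverse event. The row cannot show that.

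**Working it through.** No figure in the plan bears on this point, so the check is structural.

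**Step 1: sessions that could still be discontinued.** At most two sessions are planned per subject (Protocol 4.1).
- After the Day 1 session: 2 − 1 = 1 remains, the possible Day 43 retreatment.
- After the Day 43 session: 2 − 2 = 0 remain.

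**Step 2: where each case would appear.** The second column reads discontinuation of study drug literally, as a dose stopped or a later dose not given.

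| Case | AE-table row | SAP 5.0 disposition | Event term tied to the outcome |
|---|---|---|---|
| Double-blind event; subject leaves before Day 43 | Can be counted, because the Day 43 dose is lost | Counted, with reason | Only if the row is taken to include it |
| Double-blind event; retreatment not given; subject stays for follow-up | Counted | Not a study discontinuation | Yes |
| Day 43 session stopped part-way because of an event | Can be counted | Only if the subject also leaves | Yes |
| Open-label event after a complete session; subject leaves | Not counted | Counted, if adverse event is a recorded reason | No |

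The last line is the gap. The second line shows why disposition cannot replace the AE row, and the last shows why the AE row cannot replace disposition: they capture different subjects.

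**Step 3: the other reading.** If the SAP 6.0 convention (on treatment until study exit) were carried over to this row, an open-label exit because of an event would also end treatment and would be counted. The row would then in effect mean study exit. Neither document says which reading applies, so the same data could give two different counts.

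**Step 4: size.** The number of open-label exits missing from the AE table on the literal reading is N × r, where N is the number of subjects retreated and r the proportion leaving because of an event. The documents give neither. With purely assumed ranges of 300 to 600 for N and 0.5% to 2% for r:
- low end: 300 × 0.005 = 1.5 subjects
- high end: 600 × 0.02 = 12 subjects

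The value 600 is the whole planned enrolment and so a ceiling: SAP 4.0 provides for groups that receive no open-label treatment. These numbers illustrate scale and are not estimates.

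**The case against.** The strongest case on the other side has three parts.

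**Exits are already reported.** SAP 5.0 gives premature study discontinuation with reason, by group and period. This stands. A reader might infer that the study-drug row is the plan's only measure of withdrawal for tolerability, and the documents do not support that. What remains is that the text available does not list the reason categories, and that the disposition summary counts subjects by reason without naming the events.

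**Zero is not certain.** A reader might infer that the open-label row is zero by construction, for every retreated subject. That needs a definition of study-drug discontinuation that neither document gives. A session consists of several injections and SAP 6.0 foresees an incomplete dose, so a session stopped early could be counted; the SAP 6.0 convention could also bring study exits into the row. This stands too, and limits the claim to the literal reading. But SAP 6.0 sets a rule for exposure duration and does not define this category, so it does not settle the matter.

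**No event is lost.** SAP 10.2.3 tabulates all TEAEs by system organ class (SOC) and preferred term (PT) and lists them by subject, and serious events and deaths have their own displays. This is true, but none of these displays says which event led to exit. That link would have to be pieced together across outputs.

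It might also be inferred that double-blind events will be misclassified from site to site. The case report form and Operations Manual are not in the material, so that cannot be judged.

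**Conclusion.** The point holds as a minor, inexpensive improvement to safety reporting. The only AE-table withdrawal category concerns study drug. On the literal reading it is essentially empty for the open-label period, apart from a session stopped early, and it cannot show exits caused by adverse events. Disposition would count those exits if adverse event is a recorded reason, but the events responsible would appear in no planned table or listing.

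This rests on two things: that the undefined term is read as a dose stopped or not given, and that the disposition summary carries no event terms, as SAP 5.0 is written. How many subjects are affected cannot be derived from the documents. No efficacy endpoint, type I error or power statement is involved.

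**What to change.** In SAP 10.2.2 and 10.2.5 and Protocol 7.5:

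1. Add a category for TEAEs leading to discontinuation from the study, presented by period, with a summary by SOC and PT and a listing.
2. State that, for the double-blind period, a TEAE leading to discontinuation of study drug means that the Day 43 retreatment was not given because of the event.

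The first gives the event terms that the disposition summary lacks. The second separates subjects not retreated because of an event from those who leave the study, and from those not retreated for GL severity, pregnancy or refusal.

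The cost is one extra overview row, one table and one listing, with at most one field on the AE form to link an event to study exit. The displayed discontinuation rate may look slightly less favourable. The change concerns reporting only and leaves treatment and follow-up as they are.

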10.2.6 Possible Distant Spread of Toxin Adverse Events

PDSOT TEAEs will be summarized by PT. The PTs [REDACTED] will be based on the current MedDRA version used for the study prior to database lock.

Tabular listings of PDSOT TEAEs will be provided.

10.2.7 Neurological Assessment Adverse Events

The neurological assessment, which is comprised of a Focused Symptoms Questionnaire and a Focused Neurological Examination, will be conducted at selected study visits per protocol. Neurological assessment-associated TEAEs will be summarized by PT. The PTs will be based on the current MedDRA version prior to database lock.

Tables and listings of AEs related to the neurological assessment will be provided.

10.3 Analysis of Laboratory Data

Laboratory evaluations consisting of chemistry and hematology, and changes from baseline at each assessment timepoint will be summarized by treatment group and study period. In addition, potentially clinically important (PCI) laboratory values will be summarized.

Each laboratory value will be summarized for all time points (starting with Baseline) with the number of non-missing observations, mean and standard deviation, median, minimum, and maximum. Mean change from baseline to each applicable post-baseline visit will be summarized for each laboratory parameter, with the number of observations, baseline mean, and visit mean. The change from baseline mean, standard error, and 95% confidence interval will be presented for the mean change from baseline within each treatment group.

Changes in laboratory values will be tabulated using shift tables categorized as low, normal, or high based on the normal ranges of the laboratory used for each sample

[REDACTED]
[REDACTED]
[REDACTED].

Laboratory values will be evaluated [REDACTED]. For each laboratory PCI criterion, the number and percentage of subjects who have a post-baseline laboratory value meeting the criteria will be summarized. [REDACTED]

[REDACTED]
[REDACTED]
[REDACTED].

Listings will be provided to summarize subject-level laboratory data for subjects meeting PCI criteria.

10.4 Analysis of Vital Signs

Vital sign measurements of systolic and diastolic blood pressure, pulse rate, and temperature, and changes from baseline at each assessment timepoint will be summarized by treatment group and study period. In addition, potentially clinically important vital signs values will be summarized.

Each vital sign variable will be summarized for all time points (starting with Baseline) with the number of non-missing observations, mean and standard deviation, median, minimum, and maximum. Mean change from baseline to each applicable post-baseline visit will be summarized for each vital sign parameter, with the number of observations, baseline mean, and visit mean. The change from baseline descriptive statistics of mean, standard error, and 95% confidence interval will be presented for the mean change from baseline within each treatment group.

Vital sign variables will be evaluated based on PCI criteria [REDACTED]
[REDACTED]
[REDACTED]
[REDACTED]
[REDACTED]
[REDACTED]
[REDACTED]
[REDACTED]

[REDACTED]

[REDACTED]

Listings will be provided to summarize subject-level vital sign data for subjects meeting PCI criteria.

10.5 Safety Subgroup Analyses

Not applicable.

10.6 Other Safety Analyses

Electrocardiogram (ECG): Descriptive statistics for quantitative ECG parameters (i.e., heart rate, QRS duration, QTcB interval, QTcF interval, RR interval, and PR interval) at baseline, post-baseline, and changes from baseline values at each post-baseline timepoint will be presented.

ECG parameters are considered PCI if ECG values meet either the actual value or change from baseline PCI high criteria [REDACTED]. The number and percentage of subjects with PCI post-baseline values will be tabulated. [REDACTED]

[REDACTED]

[REDACTED]

[REDACTED]

A supportive listing of subjects with PCI post-baseline values will be provided.

Immunogenicity Assessment: Immunogenicity results, manifested as the presence of binding antibodies (positive) and neutralizing antibodies (positive) to AGN-151586, will be summarized in a table for baseline and post-baseline data. Immunogenicity findings (positive) will be tabulated with the number and percentage of subjects at each visit separately for each treatment group. Percentages will be based on the number of treated subjects with interpretable antibody assays in each treatment group at the specified visit.

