3 OBJECTIVES AND ENDPOINTS

3.1 Objectives, Hypotheses, and Estimands

Overall Objective

The objective of this pivotal study is to evaluate the safety and efficacy of AGN-151586 for the treatment of GL in subjects with moderate to severe GL.

The clinical hypotheses are:

- AGN-151586 is more effective than placebo in treating GL, as measured by both investigator and subject assessments of GL severity at maximum frown using the Facial Wrinkle Scale (FWS).
- AGN-151586 has an acceptable safety profile after single and repeat treatments.

Estimands: Primary Endpoints

The attributes of the estimands corresponding to the coprimary efficacy endpoints are summarized in Table 1. In addition, the attribute of treatment is a single dose of AGN-151586 or placebo.

Table 1. Summary of the Estimand Attributes of the Primary Efficacy Endpoints

Attributes of the Estimand				
Estimand Label	Variable (Endpoint)	Population	Handling of Intercurrent Events	Statistical Summary
Hypothetical estimand for composite primary endpoint (US FDA)	Achievement of at least a 2-grade improvement from baseline on the FWS according to both the investigator and subject assessments (composite) of GL severity at maximum frown on Day 7	Intent-to-treat (ITT) (all randomized)	Subjects who discontinue study prior to Day 7 assessments, or who do not have FWS assessments will be included in the analysis as a hypothetical scenario in which the assessments were conducted as per protocol	Response rates and rate differences between AGN-151586 and placebo treatment groups; Cochran-Mantel-Haenszel (CMH) test
Hypothetical estimand for coprimary endpoints (EU)	 Achievement of at least a 2-grade improvement from baseline on the FWS according to subject's assessment of GL severity at maximum frown at Day 7, and Achievement of at least a 2-grade improvement from baseline on the FWS according to investigator's assessment of GL severity at maximum frown at Day 7 	ITT	Subjects who discontinue study prior to Day 7 assessments, or who do not have FWS assessments will be included in the analysis as a hypothetical scenario in which the assessments were conducted as per protocol	Response rates and rate differences between AGN-151586 and placebo treatment groups; CMH test

CMH = Cochran-Mantel-Haenszel; Estimands = Secondary Endpoints; EU = European Union; FDA = Food and Drug Administration; FWS = Facial Wrinkle Scale; GL = glabellar lines; ITT = intent-to-treat; US = United States

Estimands: Secondary Endpoints

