5 STUDY ACTIVITIES

5.1 Eligibility Criteria

Subjects must meet all of the following criteria in order to be included in the study. Anything other than a positive response to the questions below will result in exclusion from study participation. Subjects who do not meet the eligibility criteria for participation in this study (screen failures) may be allowed to be rescreened. Rescreening of subjects must only occur after discussion with the sponsor. Rescreening can only occur once for any given potential subject; however, if the original screen failure was due to ineligible FWS grade(s), the subject will not be permitted to rescreen.

Disease/Condition Activity

[figure not shown]
Ø 6. Subjects must have moderate or severe GL at maximum frown as assessed by both the investigator and subject using the FWS at Screening and Baseline Day 1 Visit.

Subject History

- 7. Subjects must not have uncontrolled systemic disease.
- 8. Subjects must not have received treatment with any botulinum neurotoxin of any serotype for aesthetic treatment within the last 6 months prior to Baseline Day 1 and for therapeutic treatment within the last 12 months
- 9. Subjects do not present with or have a history of any medical condition that may place the subject at increased risk following exposure to AGN-151586 or interfere with the study evaluation.
- 10. Subjects must not have a diagnosis of myasthenia gravis, Lambert-Eaton syndrome, amyotrophic lateral sclerosis, or any other significant disease that might interfere with neuromuscular function.
- 11. Subjects must not have a history of facial nerve palsy.
- 12. Subjects must not have infection or dermatological condition at the treatment injection sites.
- 13. Subjects must not have marked facial asymmetry, dermatochalasis, deep dermal scarring, excessively thick sebaceous skin, excessively photodamaged skin, or the inability to substantially lessen facial lines even by physically spreading them apart.
- 14. Subjects must not have any eyebrow or eyelid ptosis at screening or Baseline Day 1 visit as determined by the investigator.
- 18. Subjects must not have tattoos, jewelry, or clothing which obscure the glabellar area and cannot be removed.
- 19. Subjects do not have known immunization to any botulinum neurotoxin serotype.
- 20. Subjects do not have anticipated need for surgery or overnight hospitalization during the study.

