Vital sign measurements and 12-lead ECG parameters will be summarized for each assessment timepoint, as well as for changes from baseline at each assessment timepoint. In addition, potentially clinically significant vital signs values will be summarized. Details will be provided in the SAP.

Immunogenicity results, manifested as the presence of binding antibodies (positive) and neutralizing antibodies (positive) to AGN-151586, will be summarized in a table for baseline and postbaseline data. Immunogenicity findings (positive) will be tabulated with the number and percentage of subjects at each visit. Percentages will be based on the number of treated subjects with interpretable antibody assays at the specified visit. Immunogenicity results including additional analysis of antibody response to other neurotoxin serotypes will be documented in the CSR or in a separate report.

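### The planned antibody table gives percent positive at each visit but does not show how many baseline-negative subjects became positive after dosing

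*SAP*

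**What the plan says.** Protocol 3.5 and SAP 3.4 name the presence of binding and neutralizing antibodies as a safety endpoint. The safety hypothesis in Protocol 3.1 is that "AGN-151586 has an acceptable safety profile after single and repeat treatments".

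SAP 10.6 says that binding and neutralizing results "will be summarized in a table for baseline and post-baseline data", and then: "Immunogenicity findings (positive) will be tabulated with the number and percentage of subjects at each visit separately for each treatment group". On the denominator it says: "Percentages will be based on the number of treated subjects with interpretable antibody assays in each treatment group at the specified visit". Protocol 7.5 plans the same statistic: "Immunogenicity findings (positive) will be tabulated with the number and percentage of subjects at each visit". It also says: "Immunogenicity results including additional analysis of antibody response to other neurotoxin serotypes will be documented in the CSR or in a separate report".

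The immunogenicity paragraph of SAP 10.6 shows no redaction. Neither document defines seroconversion, treatment-induced or treatment-boosted antibodies, an ever-positive count, or a cross-tabulation of baseline against post-baseline status. SAP 11.0 plans no further analyses.

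**The concern.** A percentage positive at a visit is a prevalence. It counts subjects who were positive before dosing together with those who turned positive afterwards, and each visit has its own denominator. A baseline row shows how many positives there were at the start but not whether they are the same people as the later positives. Gains and losses can cancel, and subjects positive at different visits are never accumulated.

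For an endpoint meant to inform safety after one and two treatments, the natural question is how many subjects who began negative became positive. The planned table does not answer it. The other safety domains in the SAP do relate each subject to a starting point: adverse events count only if treatment-emergent (10.2.1), laboratory values get change from baseline and shift tables (10.3), and vital signs and ECG get change from baseline (10.4, 10.6). Immunogenicity has no equivalent.

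**Working it through.** The documents state no antibody rate or precision, so there is no figure to reproduce. The only input taken from them is the group size: SAP 2.4 has 600 subjects at 3:1, and 600 × 3/4 = 450 on AGN-151586, as stated. All positivity rates below are assumptions.

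**Conversions at one later visit.** Let n be the number of subjects with a usable assay at both visits, B the number positive at baseline and Q the number positive later. If as many later positives as possible were already positive, the new positives number max(0, Q − B). If none of them were, the number is min(Q, n − B). Dividing by the n − B baseline-negative subjects gives the range of conversion rates that the visit table allows.

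| Baseline | Later visit | B | Q | New positives | Baseline-negative | Conversion rate |
|---|---|---|---|---|---|---|
| 0% | 2% | 0 | 9 | 9 | 450 | 2.00% |
| 2% | 2% | 9 | 9 | 0 to 9 | 441 | 0.00% to 2.04% |
| 2% | 4% | 9 | 18 | 9 to 18 | 441 | 2.04% to 4.08% |
| 5% | 5% | 22 | 22 | 0 to 22 | 428 | 0.00% to 5.14% |
| 10% | 10% | 45 | 45 | 0 to 45 | 405 | 0.00% to 11.11% |

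(5% of 450 is 22.5, taken as 22.) In the second row, 450 × 0.02 = 9 at each visit, 450 − 9 = 441, and 9/441 = 2.04%. The first row shows when the problem disappears: with no baseline positives and complete assays, the single-visit rate is exact.

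**Ever positive over two visits.** Suppose 0% at baseline and 2% (9 subjects) at each of two later visits. If the same nine are positive both times, 9/450 = 2.00% were ever positive. If the two sets do not overlap, 18/450 = 4.00% were. So even with no baseline positivity, visit percentages do not give cumulative incidence.

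**Both together.** With 2% at baseline and 2% at each of two later visits, the number of baseline-negative subjects ever positive lies between 0 and 18 of 441, or 0.00% to 4.08%.

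These ranges assume that the same subjects are assayed each time. The planned denominator does not require that, and where assays are missing the ranges widen, because a later positive may have no baseline result.

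**Baseline for placebo subjects treated at Day 43.** SAP 10.1 takes the safety baseline for change-from-baseline parameters as the last value before the first study drug in the study. For Placebo/AGN-151586 subjects that precedes placebo, not their first active dose. Protocol 4.1 makes the Day 43 assessments the open-label baseline. The immunogenicity paragraph does not say which applies.

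**The case against.** The strongest reply is that the endpoint is presence of antibodies and the table reports presence. It is descriptive, no test depends on it, baseline is shown by group, placebo is concurrent in the double-blind period, and conversion can be derived later from subject-level data. All of that is true. The group-level net change can be read, but it is not the number of conversions. Deriving conversion later is possible, but the definition would then be chosen after the results are seen.

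Several stronger readings are tempting and are not supported:

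- A reader might infer that later visits mix first and second exposures because placebo subjects can receive AGN-151586 at Day 43. Protocol 7.2 and SAP 4.0 and 10.1 analyse safety by treatment actually received in each period, so Placebo/AGN-151586 and AGN-151586/AGN-151586 are separate groups.
- A reader might infer from the toxin-history stratum that baseline positives are likely. Protocol 2.1 describes the serotypes as antigenically distinct, and AGN-151586 is serotype E. Protocol 5.1 imposes a washout, "Subjects must not have received treatment with any botulinum neurotoxin of any serotype for aesthetic treatment within the last 6 months", and excludes known immunization to any serotype. The text shown has no antibody-negative entry criterion, so positives are possible, but the documents do not make them probable.
- A reader might infer that the table overstates induced antibodies. It would do so only if a prevalence row were read as incidence, and the SAP does not label it that way.

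The sampling times are in Appendix D, whose table is not shown. Whether an antibody sample is drawn before dosing on Day 43, and how many post-dose samples there are, cannot be judged.

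**Conclusion.** The point holds in a limited form. The planned summary is a visit-by-visit prevalence with no within-subject comparison, so it does not identify conversion among baseline-negative subjects or the number ever positive after dosing. Pre-existing positivity is visible and exposure sequences are separated. What is missing is the comparison within subjects and a baseline-negative denominator.

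The size depends on rates that the documents do not give. Under the assumptions above it runs from no single-visit ambiguity at 0% baseline positivity to a range of about two percentage points at 2% and eleven at 10%. The cumulative count stays ambiguous even at 0% if there is more than one post-dose sample. No efficacy conclusion, alpha or power figure is affected. This is an inexpensive improvement to the reporting of a named safety endpoint, and it should be specified in advance.

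**What to change.** In SAP 10.6:

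- Add, for binding and neutralizing antibodies separately, the number and percent of baseline-negative subjects with any positive result after dosing. Present it by study period and by the sequences already defined: placebo and AGN-151586 in the double-blind period, AGN-151586/AGN-151586 and Placebo/AGN-151586 in the open-label period.
- For Placebo/AGN-151586, take as baseline the last sample before the first AGN-151586 dose (the Day 43 pre-dose sample if the schedule includes one), and state this as an exception to the safety baseline in SAP 10.1.
- Say how an AGN-151586/AGN-151586 subject who turned positive before the second dose is counted in the open-label row. Otherwise that row becomes a prevalence again.
- List baseline-positive subjects separately, and keep the by-visit table as support.

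The cost is one more baseline definition, a derived variable and one table, using antibody results that the plan already collects. In the 2% and 2% example, the range of 0 to 9 of 441 becomes a single count.
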